10.1.4 Definition of Product Complaints

Product Complaints include any written, electronic or oral communication that alleges deficiencies related to the identity, quality, durability, reliability, safety, effectiveness, or performance of a product or device after it is released for distribution. This includes all components distributed with the product(s) such as packaging, product containers, delivery system, labeling, inserts, etc.

Product Complaints may include but are not limited to issues related to:

- Appearance (eg, broken, cracks, color, particles, odor)
- Labeling (eg, missing, torn, smudged)
- Durability (eg, stability issues)
- Open packaging
- Device damage (eg, pre-filled syringe with bent needle)
- Inability of customer to understand product labeling
- Inability of customer to deliver the product successfully, including partial or incomplete delivery (eg, defective delivery system [syringe])

10.2 Reportable Events and Reporting Timeframes

The HCP is responsible for ensuring that all ADRs/SADRs, product complaints and other safety findings for any Amgen product(s) are submitted to Amgen via the supplied Amgen Safety Reporting Forms. See [Appendix 3](#) for a sample Report Form.

- All clearly documented SADRs, product complaints and other safety findings, including pregnancy and/or lactation, are to be reported to Amgen within 1 business day of the HCP's date of awareness.
- ADRs that do not meet serious criteria are to be collected in the study database and must be reported in the final study report.

11. STUDY SIZE CONSIDERATION

A total estimate of 623 patients (4,234 patient-years) will comprise the Exposed Cohort. According to the study design, the Unexposed Cohort for adult chronic ITP patients will include 1860 patients, and will account for 12,700 patient-years of follow-up ([Figure 1](#)). This is a conservative estimation.

The study will compare chronic ITP patients who received romiplostim with those patients who do not receive romiplostim. This study will collect approximately 4,234 patient-years of romiplostim-exposed patient information during the 11 years of follow-up. Although the background incidence rate of study outcomes in chronic ITP patients is unknown, this sample size has a greater than 80% probability of detecting a difference in a range of relative risks from 2 to 4 where the background incidence ranges for 0.5% to 5%.

12. STATISTICAL ANALYSIS

12.1 Data Editing

Data in the NCPRR has been collected and collated in the NHRS database, and there will be no data editing required.

12.2 Exploratory and Descriptive Analysis

Since the study is descriptive in nature for the purpose of hypothesis generation, the analyses will describe the study population and outcomes in all study cohorts, as well as in different follow-up time periods (prior to and post Nplate exposure time periods). This will include:

- Total number of subjects and total person-year observation time in each cohort in the current reporting period, and cumulative for all reporting periods
- Current incidence rates of study outcomes based on data in the current reporting period and in the cumulative data for all reporting periods
- Average platelet count in predefined romiplostim treatment periods
- Detailed descriptions of each case with increased BM reticulin and / or BM fibrosis associated with clinical signs in the current reporting period
- Detailed description of hematological malignancy cases (eg, AML) and cases of MDS

Detailed descriptions of cases with BM reticulin, BM fibrosis, hematological malignancies, secondary thrombocytopenia, or clustering of events may require a narrative description of diagnoses and therapies leading to events in order to provide context for medical interpretations. In addition, the following descriptive analyses will also be conducted:

- A tabular summary (frequency, total patient-years of observation, rate) for patients' demographic and clinical characteristics between the Exposed Cohort and Unexposed Cohort, and among inception cohorts
- A tabular summary (frequency, total patient-years of observation, rate) for baseline laboratory findings of patients between study cohorts

The romiplostim utilization pattern in adult chronic ITP patients will also be assessed (eg, demographic characteristics of users, the condition or characteristics of the disease for which the drug is used, the kind of health professional who prescribes the drug, and how patients are dosed). This descriptive analysis may also compare the utilization patterns between the romiplostim Exposed Cohort and Unexposed Cohort, as well as among inception cohorts to determine the potential selection bias. In this analysis, demographic characteristics, clinical conditions of underlying diseases, and other potential confounders will be measured and compared. Stratified analyses and a multiple regression analysis will be used as needed to determine major imbalances of patient populations between romiplostim users and non-users. The analysis will be used as the basis to determine measurable selection bias. However, non-measurable selection bias cannot be addressed by the study, which is a major limitation and adds a challenge with regard to the interpretation of study results.

12.3 Development of a Propensity Score of Romiplostim Treatment for the Chronic ITP Population

There are many factors that may affect the adult chronic ITP disease condition (eg, age, sex, length of disease, severity, platelet counts, splenectomy, co-morbidities, and concurrent medications). To reduce potential effects from confounding by indication of romiplostim therapy, a propensity score will be developed to create a pseudo-randomization in balancing important factors that might affect the outcomes between the romiplostim Exposed Cohort and Unexposed Cohort for chronic ITP patients. The propensity score is defined as the conditional probability of being treated given a set of important and relevant covariates. The logistic regression method will be used to develop the propensity score for the severity of the ITP condition. The variables to be considered may include, but are not limited to, age, sex, BMI/BSI, country, year of ITP diagnosis, length of disease, average platelet counts, lowest platelet counts, splenectomy, major comorbidities, and prior ITP medications (type and frequency), and frequency and severity of bleeding events. While the propensity score is being developed, other methods, such as stratification by country or by a span of years associated with changing practice patterns will be investigated. The aforementioned variables to be included in the propensity score development model will be updated and modified based upon the findings from an Amgen-sponsored historical study to be based upon the Danish Health Registry System Database for chronic ITP patients (Study 20070796) and expert opinions. The dependent variable for the model is romiplostim therapy (yes or no). The propensity model will be refined with every annual analysis based on newly available data. The propensity score will be reassigned to each patient for each annual analysis and the final analysis; therefore, the propensity-score for each subject in the cohorts reported in each annual and the final analysis may be different. However, variables involved in the propensity score development model will be the same throughout unless some new variable emerged during the 11-year study period. The data used to develop a propensity score will be from 6 months prior to the Index Date of receiving romiplostim therapy, and data from 6 months prior to the Index Date that is randomly selected from romiplostim-unexposed chronic ITP patients. To ensure the sensitivity and specificity of the propensity score, sensitivity analyses will be conducted for each established propensity model. The sensitivity and specificity test will be conducted using medical records for selected clinical characteristics, features, severity measures, and potential confounders.

The distribution of propensity scores for the Exposed Cohort and Unexposed Cohort will be graphically presented in a figure. Patients with very low or very high propensity scores whose scores are non-overlapping with patients in comparison cohorts will be excluded from (or trimmed from) the analysis. The “trimming” method will remove outliers from the analysis to reduce selection bias and the impact of patients with extreme conditions. This may impact the statistical power to evaluate any differences between the exposed and unexposed groups. A reduced sample size would reduce the probability of detecting a difference in a range of relative risks from 2 to 4 where the background incidence ranges from 0.5% to 5% (refer to [Appendix 1](#) for exact power). Based upon the distribution of propensity scores, 5 strata will be developed and used in the analysis. Propensity scores will also be used in multiple regression analysis as a covariate. Important variables including age, sex, ITP diagnostic year and disease duration that contribute to the propensity score can also be independently included in multiple regression analysis as additional covariates, which constitute a “Doubly Robust” model.

The propensity score, along with age, sex and diagnosis year will be used as needed to match the Exposed Cohort and Unexposed Cohort among adult chronic ITP patients.

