To address these identified and potential safety issues, Amgen is committed to establishing a comprehensive risk management program which includes cautionary instructions in the prescribing information, PV (both routine and proactive), risk management activities, and additional clinical studies. Amgen believes these actions are appropriate and adequate to manage and minimize the safety risks of romiplostim. As additional safety data becomes available from ongoing and future clinical studies and post-marketing experience, the identified and potential risks will be re-evaluated, and risk management activities will be adjusted.

The NCPRR is specifically designed to fulfill the above post-market PV requirements by the European regulatory authority. In line with these PV requirements, the study assesses acute and long latency effects of romiplostim in real-life clinical practice in three European countries for 11 years (from 01 January 2009 to 31 December 2019).

The National Health Registry System (NHRS) of Denmark, Sweden, and Norway gather all health-related data on their citizens through a complex system of interlinked databases. The Danish government, for example, has compiled nearly 200 registry databases (some initiated in the 1930s) on various datasets from medical records, hospitalization, prescriptions, laboratory and pathology results, cancer registry, and mortality to socioeconomic data on jobs and salaries. The registry databases are population-based and complete. What makes the databases a prime research tool is the fact that they can all be linked by the 10-digit personal identification number (called CPR) that follows each Danish citizen from birth to death ([Frank, 2000](#)).

Thereby the entire lifetime information of each romiplostim-exposed patient between 01 January 2009 and 31 December 2019 (11 years) can be extracted and analyzed to meet the needs of post-marketing safety surveillance. The National Health Registry databases of the 3 countries have been previously used to determine the safety profile of pharmaceuticals, and are considered to be among the best PV and epidemiology tools by regulatory authorities, epidemiologists, and safety specialists in both the medical and scientific communities.

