3.4 Selection of Participants (or Subject Eligibility)

3.4.1 Inclusion Criteria

Subjects in the NCPRR will be those whose health information is recorded by the NHRS of Denmark, Norway, or Sweden.

The eligible adult cITP romiplostim-exposed patients for the NCPRR must meet all of the following criteria:

- Patients must be 18 years or older at the time of chronic ITP diagnosis,
- Patients will have romiplostim therapy between 01 January 2009 and 31 December 2018, and
- Patients will have at least 6 months of medical information prior to initial date of receiving romiplostim treatment (Index Date), data from which will establish a baseline of study subjects.

The eligible adult cITP romiplostim-unexposed patients for the NCPRR must meet all following criteria:

- Patients must be 18 years or older at the time of chronic ITP diagnosis,
- Patients will not have received romiplostim therapy prior to or during the study period between 01 January 2009 and 31 December 2019, and
- Patients will have at least 6 months of medical information in the study period. The data from this period will establish baseline of subjects in the comparison group.

Eligible romiplostim-unexposed cITP patients will be the source of comparison cohorts for romiplostim-exposed cITP patients. Because potential confounding factors (eg, severity of ITP condition) may cause some biases for the study, however, robust propensity scoring and adjusted analyses will be essential ([Section 12](#)). In addition, appropriate contextualization from other recognized data sources will be used in comparisons to address selection biases.

In addition, according to initial dates of receiving romiplostim therapy among patients in the Exposed Cohort, the follow-up time period will be separated into 2 periods: (1) follow-up time period prior to romiplostim exposure, and (2) follow-up time period following romiplostim exposure. Patient experiences in the follow-up time period prior to the initial date of receiving romiplostim therapy will be considered as another “within-patient” comparison with the patient experiences during the follow-up time period after the initial date of receiving romiplostim therapy.

Eligible romiplostim Off-Label-Exposed patients will be any patient who received romiplostim therapy without an adult chronic ITP diagnosis.

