4.1 Sub-Patient Group Identification

The adult chronic ITP study population is identified using diagnostic codes (ICD-10: D69.3-D69.4) for at least 6 months after the first primary ITP diagnosis, and as having received at least 1 ITP medication, and/or had a splenectomy procedure during this 6-month time period. Electronic medical records will be reviewed to confirm the diagnosis. Confirmation of the diagnosis of ITP will be carried out by clinical presentations and/or related treatment. Based upon the status of romiplostim therapy, these patients will be segregated into the Exposed Cohort and the Unexposed Cohort. The index date for patients in romiplostim Exposed Cohort is defined as the first date of receiving romiplostim therapy.

The Index Date in the exposed cohort will be the date of first exposure to romiplostim. A patient who has not been exposed to romiplostim will have an Index Date imputed based upon the date of diagnosis using 2 methods: 1) if the date of diagnosis is prior to 01 April 2009, the Index Date will be imputed as 01 April 2009 (the first date of romiplostim availability), and 2) if the date of diagnosis is 01 April 2009 or later, the date of diagnosis will be imputed as the Index Date.

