7. REGISTRY FOLLOW-UP PERIOD, EXPOSURE TIME, AND TIME AT RISK FROM EXPOSURE

7.1 Registry Follow-up Period

The follow-up period will be separated into 4 periods:

- Six months prior to receiving romiplostim therapy: This period is considered a cohort qualification and baseline establishment period. Using this period, the eligibility of subjects will be challenged and confirmed, disease conditions will be assessed, and propensity scores will be assigned for each patient. Based on the information, study cohorts will be established.

- Under treatment period: The period is defined as being from Index Date to 10 days after the last dose of romiplostim medication. During this period, all study outcomes will be assessed except for outcomes related to latency effects and post treatment effects.
- Period immediately after romiplostim treatment cessation: This period is defined as between 10 to 100 days after the last dosing. The period will be used to assess risk of worsened thrombocytopenia after treatment cessation (eg, platelet counts, bleeding, as well as rescue medication usage). As needed, this study will separate this time period into 2 sub-time periods: (3a) time period from 10 to 30 days after the last dose; and (3b) time period from 30 days to 100 days after the last dose.
- Post treatment period: This is defined as the period from 100 days after the last dosing to the end of the study. This period, as well as the aforementioned 3 periods, will be used to study long term effects of romiplostim (eg, malignancies).

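### The single 6-month data window for the propensity score does not fit the history variables the score is meant to contain, so score strata and matching would adjust poorly for splenectomy, earlier ITP treatment, older bleeding and comorbidity

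*Protocol*

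**What the plan says.** Section 12.3 fixes the data source for the score in exposed patients: "The data used to develop a propensity score will be from 6 months prior to the Index Date of receiving romiplostim therapy". For the comparison cohort it uses "data from 6 months prior to the Index Date that is randomly selected from romiplostim-unexposed chronic ITP patients". Section 7.1 names the same 6 months as the baseline period, in which "disease conditions will be assessed, and propensity scores will be assigned for each patient". No other look-back is given for any score covariate.

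The candidate covariates in Section 12.3 include "length of disease, average platelet counts, lowest platelet counts, splenectomy, major comorbidities, and prior ITP medications (type and frequency"), followed by the frequency and severity of bleeding. Year of ITP diagnosis is listed as well.

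Other relevant places:
- Section 3.4.1 sets the history required of exposed patients as a minimum: "Patients will have at least 6 months of medical information prior to initial date of receiving romiplostim treatment (Index Date").
- Section 4.1 identifies chronic ITP partly by "having received at least 1 ITP medication, and/or had a splenectomy procedure during this 6-month time period", meaning the 6 months after first diagnosis. It sets the unexposed Index Date at 01 April 2009 for earlier diagnoses and at the date of diagnosis for later ones.
- Section 2.3 states that older data exist: "Thereby the entire lifetime information of each romiplostim-exposed patient" can be extracted. Section 5.1 has details of the medical history abstracted from charts.

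**The concern.** Section 8 expects romiplostim to go to patients with more severe and longer-standing disease. It wants score strata in which exposed and unexposed patients are alike in severity, duration and prior medications, and Section 3.4.1 calls robust propensity scoring essential. Splenectomy and failed earlier treatments are markers of that severity, and they are fixed by events that may lie years before the first dose. A score that sees only 6 months cannot balance them.

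The loss matters most for matching, which Section 12.3 bases on the score plus age, sex and diagnosis year: splenectomy and earlier treatment can enter only through the score. The covariates that Section 12.3 names for the doubly robust model (age, sex, diagnostic year and disease duration) do not include them either. A signal-detection comparison could then look adjusted for treatment history when it is not.

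**Working it through.** The plan gives no figure on this point to reproduce. The check has four parts.

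**1. Share of prevalent patients (Section 3.5).** 7410 × 0.20 = 1482; × 0.95 = 1408; × 0.25 = 352 exposed. 5700 × 0.20 = 1140; × 0.95 = 1083; × 0.25 = 271 exposed. Total exposed 623, and 352/623 = 57% are prevalent. Unexposed: (1408 − 352) + (1083 − 271) = 1056 + 812 = 1868 (the plan states 1860), of whom 57% are prevalent.

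**2. What the window can see.**
- Prevalent unexposed patients have an Index Date of 01 April 2009, so the window runs from 01 October 2008 to 31 March 2009. The qualifying treatment period is the first 6 months after diagnosis. Anyone diagnosed before 01 April 2008 therefore has it wholly before the window. With diagnoses assumed uniform over 1996–2008, that is 12.25/13 = 94%.
- Unexposed patients diagnosed from 01 April 2009 have diagnosis as their Index Date. If this means the first ITP diagnosis, the window precedes any ITP treatment. Across all unexposed patients, the share with no qualifying treatment in the window is then 0.57 × 0.94 = 53% if the date means chronic ITP diagnosis, and up to 97% if it means first diagnosis.
- For exposed patients the capture share must be assumed. Assumptions: prevalent diagnoses uniform over 1996–2008 with first dose April–December 2009; incident diagnoses uniform from 2009 to mid-2018 with first dose after 0.5 year plus an exponential delay of mean 2 years; splenectomy at an exponential time after diagnosis, mean 0.5 to 4 years. The window then holds 2–5% of pre-dose splenectomies in prevalent users and 17–24% in incident users. Weighted 352:271, this is about 8–13%, so 10% is used below.

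**3. Confounding left by one truncated binary history.** Let pE and pU be the prevalence in exposed and unexposed patients, RR the risk ratio and s the share captured. Uncaptured events are treated as no event.
- Crude = [1 + pE(RR − 1)] / [1 + pU(RR − 1)]
- Prevalence among unflagged unexposed: q = pU(1 − s)/(1 − pU·s)
- Expected, standardised to the exposed: E = pE·s·RR + (1 − pE·s)[1 + q(RR − 1)]
- Remaining = [1 + pE(RR − 1)] / E

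With pE = 0.5, pU = 0.2, RR = 2 and s = 0.10: crude = 1.5/1.2 = 1.25; q = 0.18/0.98 = 0.184; E = 0.10 + 0.95 × 1.184 = 1.224; remaining = 1.5/1.224 = 1.225.

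| RR | Crude | 10% captured | 25% captured | 50% captured | Full history |
|---|---|---|---|---|---|
| 1.5 | 1.14 | 1.12 | 1.10 | 1.07 | 1.00 |
| 2 | 1.25 | 1.23 | 1.19 | 1.13 | 1.00 |
| 3 | 1.43 | 1.38 | 1.31 | 1.20 | 1.00 |

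With other assumed prevalences (30–50% v 10–20%) and RR 1.5–3, the part of this one factor's confounding that remains on the log scale is 93–97% at 4–6% capture, 72–78% at 25% and 46–54% at 50%.

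**4. Total confounding when other covariates survive.** A simulation used five score strata with splenectomy, disease duration and platelet count all driving treatment and outcome (splenectomy risk ratio 2, correlation between the three varied). Only splenectomy was truncated, with 0–25% captured. Crude confounding was 1.27–1.97. With full splenectomy history, 9–11% of it remained on the log scale; with the 6-month window, 23–47%. Truncating prior treatments and comorbidities as well would leave more.

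**The case against.** The best defence is that the window need not be read literally. Year of diagnosis and length of disease are in the same list and cannot be confined to 6 months. Section 7.1 can mean that status is assessed at baseline, and a past splenectomy can be a baseline status. Six months in Section 3.4.1 is a minimum, Section 5.1 abstracts medical history, and no coding rule is given. This stands in part. A reader might infer that older events will be scored as absent; the protocol does not say so. What it does say is a data window that conflicts with its own variable list, and a programmer following it would lose the older events.

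A reader might also infer that confounding by indication stays almost uncorrected. The documents do not support that. Age, sex, country, diagnosis year, disease length, recent platelet counts and recent bleeding survive the window. Section 6.3 lists splenectomy and comorbidities as analysis variables, Section 12.4 adjusts for confounders as well as the score, and Section 12.7 allows stratification by splenectomy and history of significant bleeding. Section 3.4.2 already excludes the Appendix 2 conditions at any earlier time. These routes are real, but the Section 12.4 model and the Section 12.7 strata apply as needed, and matching on the score does not use them.

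Finally, comparisons are exploratory and Section 13 concedes that the score may be inadequate. That lowers the severity. It does not justify an avoidable loss of data in an analysis used for signal detection.

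**Conclusion.** The point holds as a moderate one. The 6-month window and the history covariates in Section 12.3 do not fit together. Followed as written, the window would lose the older history of most prevalent patients, who are 352 of the 623 expected exposed. Score strata and matching would then adjust poorly for those factors.

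For a single history variable at 10% capture, confounding of 1.25 falls only to about 1.23 (1.12 to 1.38 remaining for risk ratios 1.5 to 3). Total confounding is reduced further: 23–47% remains in the illustration, against 9–11% with full splenectomy history. The prevalences, risk ratios and splenectomy timing are assumptions, since the protocol gives none, so these figures show scale and are not forecasts.

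The primary objective, an incidence rate in exposed patients, does not use the score and is unaffected. The unexposed Index Date adds to the problem: Section 12.3 reads as a randomly selected date and Section 4.1 fixes it by rule, so what the window covers may differ between cohorts.

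**What to change.** In Sections 12.3 and 7.1, state the look-back by type of variable:
- **Current state** (platelet counts, current medication, recent bleeding): the 6 months before the Index Date.
- **History** (splenectomy, number and type of prior ITP treatments, bleeding history, thromboembolic history, comorbidities): all available registry and chart data up to the Index Date, with the same look-back start in both cohorts within each country.

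Reconcile Sections 4.1 and 12.3 on how the unexposed Index Date is set, and say whether the date of diagnosis means first ITP diagnosis or chronic ITP diagnosis. A longer look-back alone does not cure the asymmetry if an unexposed patient's Index Date precedes all ITP treatment.

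The cost is mainly wording in the protocol and the analysis plan, because Section 2.3 describes the registries as linkable and Section 5.1 already abstracts medical history. The lifetime-data sentence in Section 2.3 refers to exposed patients, so equal availability for unexposed patients should be confirmed. The downside is that look-back length may differ by country; a common start date within country, or look-back length as a covariate, handles that.
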